6.3.1.3.1 Seriousness

An SAE is defined as any untoward medical occurrence that at any dose:

- Results in death
- Is life-threatening. This means that the patient is at risk of death at the time of the event. It does not mean that the event hypothetically might have caused death if it were more severe
- Requires inpatient hospitalisation or prolongation of existing hospitalisation
- Results in persistent or significant disability or incapacity
- Is a congenital anomaly or birth defect
- Is an important medical event that may not be immediately life-threatening or result in death or hospitalisation but that may jeopardise the patient or require intervention to prevent one of the above outcomes. Examples of such events are intensive treatment in an emergency room or at home for allergic bronchospasm; blood dyscrasias or convulsions that do not result in hospitalisation; or development of drug dependency or drug abuse

“At any dose” does not imply that the patient is receiving study treatment at the time of the event. Study drug doses may have been given during treatment cycles or interrupted temporarily prior to the onset of the SAE, but may have contributed to the event.

6.3.1.3.2 Intensity

Classical reporting of mild, moderate and severe AEs making a reference to the patient's functional status is difficult for a randomised study in critically ill patients. Patients enrolled in this study will primarily be mechanically ventilated and comatose due to their underlying condition and/or the drugs they are prescribed for sedation and analgesia in the ICU. Therefore, the classical approach to AE reporting, which requires patient communication and evaluation of the impact on functioning will be adapted to the ICU environment. The Investigator will be responsible for the assessment of severity, using the categories of mild, moderate or severe to describe each AE as:

- **Mild:** Does not interfere with patient's usual function
- **Moderate:** Interferes to some extent with patient's usual function
- **Severe:** Interferes significantly with patient's usual function

Note the distinction between serious and severe AEs. **Severe** is a measure of intensity whereas an event must meet one of the criteria for serious events listed in Section 6.2.1.3.1 to be considered **serious**; thus, a **severe** reaction is not necessarily a

serious reaction. For example, a headache may be severe in intensity, but would not be classified as serious unless it met one of the criteria for serious events listed in Section 6.2.1.3.1.

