6.3.1.4 Recording Adverse Events

AE reporting will extend from signing of informed consent. AEs occurring after D30 should be reported to the Sponsor by the Investigator if the Investigator considers there is a causal relationship with the study drug. However, all deaths will be recorded and reported as SAEs throughout the study (up until D90).

All AE reports should contain a brief description of the event, date and time of onset, date and time of resolution, intensity, treatment required, relationship to study drug, action taken with the study drug, outcome, and whether the event is classified as serious.

Recording a diagnosis (when possible) is preferred to record a list of associated signs and symptoms. However, if a diagnosis is known but there are associated signs or symptoms not generally attributed to the diagnosis, the diagnosis and each sign or symptom must be recorded separately.

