13.1 Adverse events

All recorded adverse events will be coded according to the Medical Dictionary for Regulatory Activities (MedDRA). Treatment emergent adverse event (TEAE) is defined as an AE that begins or worsens in severity after at least one dose of study drug has been administered. Non-treatment emergent AEs are listed only.

TEAEs will be summarized using frequency and subject based tables. TEAEs will be tabulated by treatment group, system organ class (SOC), preferred term (PT), causality and severity. For analysis purposes, each subject will also be categorized by the maximum severity reported for a given TEAE and these will be tabulated by maximum severity. TEAEs will be summarized separately for treatment period (D1-D5) and short-term follow-up period (D6-D30). TEAEs are not collected, and therefore not reported, during the mid-term follow-up.

Serious adverse events (SAEs) and AEs leading to discontinuation will be summarized by treatment groups. All deaths up to D90 are reported as SAEs.

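### AE severity is graded by usual function in a mostly ventilated, comatose population, although the protocol calls this difficult and announces an ICU adaptation that neither document supplies

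*Protocol*

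**What the plan says.** Protocol 6.3.1.3.2 (Intensity) opens by saying that the usual mild/moderate/severe reporting, "making a reference to the patient's functional status is difficult for a randomised study in critically ill patients". The reason follows: "Patients enrolled in this study will primarily be mechanically ventilated and comatose", because of the underlying condition or of drugs given for sedation and analgesia. It concludes: "Therefore, the classical approach to AE reporting, which requires patient communication and evaluation of the impact on functioning will be adapted to the ICU environment".

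Its next sentence makes the Investigator responsible for the grade. Three definitions follow, all on one criterion. Severe, for example, reads "Interferes significantly with patient's usual function"; moderate is interference to some extent, and mild is none.

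The SAP does not define severity and uses it as recorded. Section 13.1 states: "TEAEs will be tabulated by treatment group, system organ class (SOC), preferred term (PT), causality and severity". It adds each subject's maximum severity for a given TEAE, and separate summaries for the treatment period and for D6 to D30. Protocol 6.3.1.2 and SAP 13.1 also count an AE as treatment emergent if it worsens in severity after dosing.

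Protocol 6.3.1.4 requires every AE report to include, among other items, "intensity, treatment required, relationship to study drug, action taken with the study drug".

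**The concern.** The section gives a reason for not grading by function, announces a change, and then grades by function. The only visible change is that the Investigator assigns the grade, and that does not alter what is being graded. A deeply sedated, ventilated patient has no usual function to observe.

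Read literally, an event in such a patient interferes with nothing and is mild. An Investigator who instead imagines the patient awake would grade the same event higher. Grades are therefore likely to be too low, or to depend on how each Investigator fills the gap.

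The period most exposed is the one in which the drug is given. Protocol 5.8 expects fever, tachycardia and rigor mostly soon after administration. It names sedatives among the ways these may be managed, so handling an event can itself change the function on which its grade depends.

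**Working it through.** No sample size, power or alpha is involved. The check compares passages and counts tables.

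**1. Rationale against definitions.** Protocol 6.3.1.3.2 sets aside reliance on patient communication and on the effect on functioning. All three grades then rest on the effect on functioning. None refers to treatment given, organ support, laboratory thresholds or any other feature visible in a sedated patient.

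**2. Is there another scale?** Protocol 6.3.1.3 and 6.3.1.3.4 do adapt AE reporting to the ICU. They decide what counts as an AE (for example, a common ICU aberration that needs significant intervention), not how severe it is. Protocol 8.4 and SAP 13.1 use severity without defining it. No other scale appears in either document.

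**3. What depends on the scale.** From the table plan in SAP 19.3:

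| Block | TEAE tables | Of which use severity |
|---|---|---|
| Overall, 14.3.3.1 to .6 | 6 | 4 (.3 to .6) |
| Treatment period, 14.3.4.1 to .6 | 6 | 4 (.3 to .6) |
| Short-term follow-up, 14.3.5.1 to .6 | 6 | 4 (.3 to .6) |
| Total | 6 + 6 + 6 = 18 | 4 + 4 + 4 = 12 |

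So 12 of the 18 tables in these blocks use the grade.

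**4. TEAE definition.** AEs are recorded from consent (Protocol 6.3.1.4), before the first dose. An event already present at dosing becomes treatment emergent only if it worsens in severity, which is a judgement on the same scale. If it is judged not to have worsened, SAP 13.1 places it among events that are only listed. The number of such events is not given.

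**5. How the weakness varies.** It is clearest in the four treatment-period tables. It is least in the four D6 to D30 tables, when some patients will be awake, and mixed in the four overall tables. The documents give no share of patients sedated by day, so the loss of information cannot be turned into a number.

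**6. What is available instead.** Whether treatment was required is on every AE report (Protocol 6.3.1.4), yet no table title in SAP 19.3 uses it. Action taken with study drug is also recorded. A table of it would largely repeat Table 14.3.7 (TEAEs leading to discontinuation), because Protocol 5.2 allows neither dose modification nor temporary cessation.

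**The case against.** The strongest reply is that a reader could infer far more than the text supports. Most of that reply stands.

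- *Severity cannot be judged at all, so all twelve tables are nearly empty.* The protocol says difficult, not impossible, and says patients are primarily, not always, ventilated and comatose. It foresees ICU discharge within the treatment period (3.1, 7) and spontaneous reports from conscious patients (3.2.2). It promises an adapted approach to reporting, not literally a new scale.
- *Severity is the only graded safety measure.* It is not. Seriousness and three-level causality are recorded for each AE. SAP 13.2 and 13.3 plan laboratory range and shift tables, and vital signs with maximum change. Fever, tachycardia and liver enzyme rises, all anticipated in Protocol 5.8, are covered there objectively.
- *The same event may be called mild or severe with equal support from the text.* The definitions ask whether the event interferes with function. If sedation removed the function, the event did not. The literal reading leans towards mild, so the problem is under-grading and vagueness.
- *The grades are biased between arms.* Sites are blinded, so inconsistent grading is expected to act mainly as noise. Sedation might differ by arm, but nothing in the documents shows that it did.

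Grading guidance could also sit in the eCRF completion instructions (Protocol 9.1.1) or the Safety Management Plan (6.3.1.5), which are not among the documents. Section 6.3.1.3.2 points to neither for grading.

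None of this removes the contradiction within 6.3.1.3.2, or supplies a meaning for the grades in a sedated patient.

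**Conclusion.** The point holds in a limited form. By the protocol's own reasoning its severity scale fits poorly the patients it expects to treat, and the announced adaptation is absent from both documents. Twelve planned tables, above all 14.3.4.3 to 14.3.4.6, and the worsening part of the TEAE definition rest on grades with no workable meaning for a sedated patient.

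This is worth correcting but does not threaten the trial's main result. D30 mortality is unaffected, no test or stopping rule set out in the documents uses severity, and the other safety measures remain. The conclusion assumes that many patients are sedated during dosing, as the protocol expects, and that no unseen document supplies ICU grading rules. The size of the loss and any difference between arms are unknown.

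**What to change.** **For the report of this trial.** SAP section 2 records that the study was discontinued after the interim analysis, so grades already collected cannot be changed. Two SAP changes can still help:

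1. Add to 13.1 and 19.3 one TEAE table by arm, split by whether treatment was required.
2. Footnote the severity tables, above all 14.3.4.3 to 14.3.4.6, as of limited meaning for events graded while the patient was sedated. If grading guidance exists elsewhere, cite it there.

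A table of action taken with study drug is not needed.

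**For the protocol text, including any reuse.** Define the grades in 6.3.1.3.2 by features observable in a sedated patient. For example: mild, no intervention needed; moderate, treatment or closer monitoring needed; severe, new or escalated organ support or urgent intervention needed. This extends the intervention threshold already in 6.3.1.3. Keep the wording apart from the seriousness criteria, since 6.3.1.3.2 itself insists on that distinction. Its cross-reference to 6.2.1.3.1 for those criteria should read 6.3.1.3.1.

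**Cost.** One descriptive table from a field already collected, footnotes, and one protocol paragraph. The new table may discriminate only modestly, because many ICU aberrations become AEs only if they need intervention. Events graded on a new scale would have to be shown separately from those on the old one.

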6.3.1.3.3 Causality

The Investigator will assess the causality/relationship between the study drug and the AE and record that assessment in the eCRF. Causality will be assessed as:

- **Not related:** AE is obviously explained by another cause; or the time of occurrence of AE is not reasonably related to administration of the study drug
- **Possibly related:** Study drug administration and AE occurrence are reasonably related in time; and AE is explained equally well by causes other than study drug
- **Probably related:** Study drug administration and the occurrence of the AE are reasonably related in time; and the AE is more likely explained by exposure to study drug than by other mechanisms

The most likely cause of an AE (e.g., disease under treatment, concomitant disease, concomitant medication, other) will be indicated in the eCRF with details of the concomitant disease or medication or other cause.

6.3.1.3.4 Clinical Laboratory Adverse Event

Abnormal laboratory findings (e.g., biochemistry, haematology, urinalysis) or other abnormal assessments (e.g., vital signs) that are judged by the Investigator as clinically significant will, if certain requirements are met, be recorded as AEs or SAEs. Clinically significant abnormal laboratory findings or other abnormal assessments that meet the definition of an AE or SAE and are detected during the study, or are present at baseline and significantly worsen following the start of the study, will be reported as AEs or SAEs. However, clinically significant abnormal laboratory findings or other abnormal assessments that are associated with the disease being studied (unless judged by the Investigator as more severe than expected for the patient's condition), or that are present or detected at the start of the study and do not worsen, will not be reported as AEs or SAEs.

The Investigator will exercise their medical and scientific judgment in deciding whether an abnormal laboratory finding or other abnormal assessment is clinically significant.

6.3.1.4 Recording Adverse Events

AE reporting will extend from signing of informed consent. AEs occurring after D30 should be reported to the Sponsor by the Investigator if the Investigator considers there is a causal relationship with the study drug. However, all deaths will be recorded and reported as SAEs throughout the study (up until D90).

All AE reports should contain a brief description of the event, date and time of onset, date and time of resolution, intensity, treatment required, relationship to study drug, action taken with the study drug, outcome, and whether the event is classified as serious.

Recording a diagnosis (when possible) is preferred to record a list of associated signs and symptoms. However, if a diagnosis is known but there are associated signs or symptoms not generally attributed to the diagnosis, the diagnosis and each sign or symptom must be recorded separately.

6.3.1.5 Reporting Serious Adverse Events

According to applicable European Union regulations and requirements, an SAE must be reported to the Sponsor from the trial site as soon as possible **within 24 hours** of becoming aware of the SAE. A medically qualified person at the trial site identified on the Delegation of Authority Log with this responsibility must assess the SAE. Any member of the clinical trial site staff can assist in reporting an initial SAE. The Principal Investigator or delegated sub-investigators are responsible for the SAE reporting procedures at the site during the trial, and must always sign-off on each SAE even if other site staff have reported the event on behalf of the investigators. A delegation log at each trial site will clearly show delegation of responsibilities regarding SAE reporting.

The SAE form must be completed with all the relevant information and forwarded to Crown Pharmacovigilance by:

- Email: [REDACTED]
- or*
- Fax: [REDACTED] In case of delivery failure, please **call:** [REDACTED]

If the SAE is urgently reported by telephone, a paper SAE form must always be completed and forwarded to Crown Pharmacovigilance as soon as possible.

The Investigator and the Sponsor (or Sponsor's designated agent) will review each SAE report and the seriousness and the causal relationship of the event to study treatment will be evaluated. In addition, the Sponsor (or Sponsor's designated agent) will evaluate the expectedness according to the reference document (Investigator Brochure). Based on the Investigator and Sponsor's assessment of the event, a decision will be made concerning the need for further action.

If consensus on the assessment cannot be reached between the parties (e.g., Investigator and Sponsor/Sponsor's delegate), all opinions will be provided in the Council for International Organizations of Medical Sciences Form I report and reporting to the CA and IEC should be based on the highest degree of causality provided.

Details for reporting SUSARs can be found in Section 6.3.1.7.

All SAEs will be recorded that occur between signing of informed consent and D30. Events occurring after D30 and coming to the attention of the Investigator should be reported only if they are considered in the opinion of the Investigator to be causally related to the investigational drug. However, all deaths up to D90 will be reported as SAEs.

All SAEs occurring as described above, must be reported **within 24 hours** by email or fax to Crown Pharmacovigilance.

The minimum information required for an initial report is:

- Details of person sending the report (i.e., name and address of Investigator)
- Patient identification details (screening/randomisation number, age, sex, NOT patient name)
- Protocol number
- Description of SAE
- Causality assessment

However, all points on the SAE form should be covered in the initial report and the completed SAE form itself must be emailed or faxed to Crown Pharmacovigilance.

After receipt of the initial report, Crown Pharmacovigilance will review the information and, if necessary, contact the Investigator to obtain further information for assessment of the event. Crown CRO will be responsible for all information processing and reporting according to local legal requirements.

Detailed instructions concerning SAE reporting procedures will be described in a Safety Management Plan written by Crown Pharmacovigilance. SAE Report Form and contact information for reporting SAEs will be provided to the sites.

6.3.1.6 Follow-up of Adverse Events

All AEs experienced by a patient, irrespective of the suspected causality, will be monitored until: the AE has resolved; any abnormal laboratory values have returned to baseline or stabilised at a level acceptable to the Investigator and Medical Monitor; there is a satisfactory explanation for the changes observed; the patient is lost to follow-up; or the patient has died.

6.3.1.7 Suspected Unexpected Serious Adverse Reactions

Any AE that is serious, associated with the use of the study drug, and unexpected (SUSAR) has additional reporting requirements, as described below.

- If the SUSAR is fatal or life threatening, associated with use of the study drug and unexpected, regulatory authorities and IECs must be notified **within 7 calendar days** after the Sponsor learns of the event. Additional follow-up information (cause of death, autopsy report and hospital report) should be reported **within an additional 8 days** (15 days total).
- If the SUSAR is not fatal or life threatening but is otherwise serious, associated with the use of the study drug and unexpected, regulatory authorities and IECs must be notified **within 15 calendar days** after the Sponsor learns of the event.

The Sponsor will notify the Investigators in a timely fashion of relevant information about SUSARs that could adversely affect the safety of patients. Follow-up information may be submitted if necessary.

The Sponsor will also provide annual safety updates to the regulatory authorities and IECs responsible for the study. These updates will include information on SUSARs and other relevant safety findings.

6.3.1.8 Pregnancy

Monitoring of pregnancies is not applicable to this study because pregnancy is an exclusion criterion and a pregnancy test is performed in all women of childbearing potential at screening. Owing to the nature of the study involving short (6-day) treatment with the study drug in an ICU setting, it is not possible for women to become pregnant during treatment and for there to be any foetal exposure to the study drug.

6.3.2 Laboratory Variables

The biochemistry and haematology analysis will be performed at the hospital laboratories of the individual Investigator sites. These analyses are mostly included in the standard care of RAAA patients. Copies of laboratory accreditation and relevant

reference ranges will be provided to the Sponsor or representative prior to the analysis of the first patient sample at that site.

The laboratory variables measured in the study will be as detailed in Table 2.

Blood samples for determination of biochemistry and haematology will be taken at pre-dose on D0 (baseline value), D1, D2, D3, D4, D5, D6, D9, D13 and D30 (or on a particular date if a patient is discharged from initial operating hospital or discontinues from the study after D6 but prior to D30), as detailed in the study flow charts in Tables 5 & 6. Patient is not invited to laboratory visit, once discharged from hospital, except on D30 for assessment of NABs. The date and time of collection will be recorded in the eCRF.

Table 2: Laboratory Variables

Biochemistry	Haematology Includes coagulation	Other
Alanine transaminase (ALAT) Alkaline phosphatase (AFOS) Aspartate transaminase (ASAT) Bicarbonate Lactate pH Bilirubin Calcium Creatinine Potassium Sodium (blood gas value acceptable)	Haemoglobin Leucocyte differential count (absolute) Mean cell volume Platelet count Red cell count White cell count	Pregnancy test

Total volume of blood required for biochemistry and haematology samples per patient are shown below in Table 3.

Table 3: Total Volume of Blood required for Biochemistry/Haematology Samples

Assessment	Number of Samples	Per Sample Volume (mL)	Total Volume (mL)
Biochemistry	9	6	56
Haematology	9	9	81
Pregnancy test	1	4	4
			141

6.3.3 *Vital Signs*

Vital signs are recorded at D0 pre-dose (baseline) and continuously during ICU stay, and at least daily during hospital care. Reporting points D0 pre-dose (0 hrs), D1, D2, D3, D4, D5, D6, D9, D13 and D30 (or on a particular date if a patient withdraws from the study after D6 but prior to D30), as detailed in the study flow charts. The date and time of collection of each parameter will be recorded in the eCRF.

Vital sign variables include:

- Blood pressure (BP) (mmHg): to be recorded intra-arterially or using a device with an appropriate cuff size for the patient.
- Heart rate (HR) (bpm): measured as per clinical practice on each ICU
- Temperature (C°): auricular (preferred, but other clinically used routine methods are also acceptable) temperature

6.3.4 *Physical examination*

A physical examination covering the major organ systems will be performed at screening (baseline) and D30 (or when a patient is discharged from the hospital prior to D30).

At screening the physical examination also includes:

- predicted body weight if actual weight is not attainable. Patient reported weight is acceptable. Calculate the predicted body weight (kg) using the following formulae:
 - i. ♂ $50 + 0.91(\text{height in cm} - 152.4)$
 - ii. ♀ $45.5 + 0.91(\text{height in cm} - 152.4)$
- actual height (in cm) reported by patient

6.4 **Baseline characteristics and disposition**

As per Study Flow Chart baseline assessments consist of those assessments carried out after the informed consent has been obtained in the screening period and those carried out prior to the first dose of study medication on D0. Peri procedural information is collected as it may have impact on the patient outcomes. These include duration of the surgical procedure for RAAA, total clamping time, total bleeding volume, total volume substitution, total blood substitution, total red blood cells substitution, total platelets substitution, total crystalloids substitution and total diuresis volume during procedure. Recycling of blood during surgery (yes/no).

Demographic and baseline characteristics are summarised by treatment group and overall. Statistical comparisons are undertaken to compare treatment groups for any of these parameters.

Disposition and reasons for discontinuation are summarised for all patients together with treatment exposure and study duration by treatment group.

6.5 **Pharmacoeconomic Evaluation**

To calculate the expected incremental cost effectiveness of intravenous FP-1201-lyo compared with standard care in the treatment of patients with RAAA and performed open aortic repair, the following parameters will be measured/collected:

- AEs between the first dose of study medication at D0 0 pre-dose and D30

- concomitant medications and therapies as recorded from Screening to D30
- the number of days in ICU from D0 pre-dose to D30
- the number of days in hospital from D0 pre-dose to D90 (3 months)
- the number of days at another health care facility from D0 pre-dose to D90
- the number of days on haemodialysis from Screening to D30 and D90
- the number of organ failure free days from D0 pre-dose to D30
- the number of VFDs from D0 pre-dose to D30

